1.a. *Services Research on Interim Opioid Maintenance* (9/20/2001 – 7/31/2005). The original R01 was an RCT that compared IM to waiting list for 319 participants. The study had follow-up rates of 92.5% and 91.2% at 4-month and 10 months, respectively. Participants randomly assigned to the waiting list (treatment as usual at that time) were far less likely to enter standard MM and far more likely to continue to use heroin, commit crimes,^{23,24} exhibit HIV sexual and drug use risk behavior while high,⁷⁶ and to be arrested (as determined by official arrest records).¹⁸ Findings were widely disseminated at national research and practitioner meetings and featured in NIDA Notes and other secondary outlets.

1.b. *Scaling Up Interim Methadone* (7/15/2004 – 7/14/2005; CSAT grant). The PI and his team helped Baltimore's substance abuse authority (BSAS) to obtain a grant to expand IM at 6 MMPs to address ongoing waiting lists. During an 18-month period, over 1,000 patients were enrolled in IM, of whom 76.2% successfully transferred to standard MM.⁷⁷ For patients who transferred, opioid-positive tests decreased from 89.6% to 38.4% from admission to transfer. Following this project IM became a part of Baltimore's treatment system.

1.c. *Entry into Comprehensive Methadone Treatment via Interim Maintenance* (6/1/2007-5/31/2012). This competing continuation was an RCT conducted at two community-based MMPs. Adults on MMP waiting lists ($N = 230$) were randomly assigned to either 4 months of IM followed by 8 months of standard methadone (SM) or to SM for 12 months. At one site, a third condition, restored methadone (RM), was included in the random assignment; its counselor had half the number of patients as the counselors in the SM condition. Participants were interviewed at baseline, and at 2, 4, and 12 months post-baseline, assessing enrollment and retention in standard MM, heroin and cocaine use, self-reported HIV-risk, earnings, hospitalizations, criminal activities, and incarcerations. The follow-up rates for the IM, SM, and RM conditions were: 97.9%, 89.4%, and 96.3% at 4 months; and 93.9%, 88.5%, and 92.5% at 12 months.

Key Findings:

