passes), housing challenges, and fluctuating motivation. Gender-specific issues will be addressed, such as obtaining child care and referrals to treatment for drug using significant others. PNers will arrange to meet the participant at the selected MMP for the first visit to maximize the likelihood of keeping the appointment. PNers will remain with the participant during the intake process to assist in communication with the MMP if necessary and to advocate for the participant. They will also facilitate keeping treatment appointments through reminders, coaching, and if necessary, meeting the participant either at the MMP or in the community to accompany them. The PNers will call participants who miss appointments to determine what happened and to facilitate another appointment or referral. PNers will seek out participants if they cannot be reached by phone (much the same way that our research staff now does for follow-up interviews using extensive locator information).

Once a participant is enrolled in treatment, the PNer will assist them (if necessary) in gaining an ID card and will provide them with bus or train tokens for the first few weeks until a reduced fare bus pass can be obtained. If necessary, navigators will assist the participant in complying with the instructions provided by the clinic staff in completing required documentation to obtain Medicaid or Maryland's state health benefits that will pay the clinic for treatment, whether MM or some other modality. Limited funds will be available for the PNers to obtain bus tokens, and to pay for ID cards and other needed low-cost services.

It is anticipated that the PNers will meet with the participants weekly during the first month, and about every other week (or more) during the second and third months, as needed. Phone calls will be made in between appointments or used as reminders or to seek the participant out if appointments are missed.¹⁰³ As needed, the PNers will go into the community to find the participant at their home or usual hangouts to try to reengage them following the procedures that we use successfully in tracking this population for research follow-ups. The PNers will enter in an excel database and written progress notes all of their participant-related activities including all attempts at contacting participants, PN services delivered, site of PN services, referrals made, and community services received.

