Follow-up and Attrition: Consistent with the parent study^{25,26} and our prior research with opioid-dependent patients^{23,24} we will collect detailed locator information, including cell phone numbers (for calls or texts), contact information for relatives and peers, and names and addresses of participants' "hang-outs." We will also, with permission of the participant, collect email addresses and social media contact information (e.g., facebook; Twitter) in order to contact the participant. When unable to contact participants via phone, the RAs will track the participants in the community through our successful and robust procedures for participant tracking. Thus, we expect to obtain follow-up rates of about 90%, consistent with our previous studies in Baltimore City with out-of-treatment opioid dependent individuals^{23,24,105} and the parent study.^{25,26} The PI and his staff have located over 90% of participants at 10-month follow-up for the first study of Interim Methadone, and at 12 months in both the parent study, and in the RCT of methadone for prisoners.³⁹

Measures: Figure 1 shows a schedule of the measures corresponding to each study aim.

Figure 1. Data Collection Schedule and Measures by Aim

Measures	Baseline	Follow-up
Aims 1-2: To compare IM + Patient Navigation v. IM alone v. Methadone Detoxification (Enhanced Treatment-as-Usual) on: treatment entry and retention, illicit opioids and cocaine use, DSM-5 criteria for opioid and cocaine use disorders; HIV-risk behaviors, criminal activity, arrest, and incarceration.		
Treatment Entry (self-report from Methadone Treatment Exposure form))		1 month
Enrolled in Treatment (self-report from Methadone Treatment Exposure form)*		3, 6, & 12-month
Illicit Opioid and Cocaine Use (ASI and urine drug testing)	◆	1,3, 6, & 12-month
DSM-V Criteria of opioid and cocaine use disorder (modified WMH CIDI)	◆	3- 6, and 12-month
Criminal Behavior (ASI)	◆	1,3, 6, & 12-month
Arrests and Incarcerations: Self report and criminal justice records	◆	12-month
HIV Risk Behavior (RAB)	◆	6, & 12-month
Overdose AE Form		1,3, 6, & 12-month
Methadone Treatment Exposure Questionnaire		1,3, 6, & 12-month
Quality of Life (WHOQOL-BREF)	◆	1,3, 6, & 12-month
Aim 3: To conduct a cost-benefit analysis of the relative costs of the three study Conditions		
Economic Form 90 (Health care utilization)	◆	3, 6, & 12-month
Substance Abuse Services Cost Analysis Program (SASCAP)		†

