Arrest and incarceration (Criminal Justice Records)	◆	12-months only

* Participants transitioning directly to other community MMPs or buprenorphine treatment will be considered still in treatment.

† Consistent with prior research, the SASCAP will be administered once during the treatment phase.

Participants will be paid \$30 for follow-up interviews (regardless of whether they are conducted in the community or during a re-incarceration) and will provide consent for research staff to check hospital and arrest records. Participants who are interviewed for follow-up during a re-incarceration will have the option to receive their \$30 deposited into their jail or prison account or to have a money order mailed to a designated person. They will not be paid for the baseline interview conducted in jail to avoid the perception of coercion.

Longer-term follow-ups: Participants will be asked (using a consent form addendum) if they'd be willing to have a 24-month follow-up interview for which they would be paid \$40. The 24-month interviews will include the same assessments as the 12-month interviews described above. In addition they will be asked if the research team could contact them beyond the 24-month follow-up for further informed consent for even longer-term follow-up interviews.

Measures for Aim 1 and 2:

Entry into Treatment: within the first 30 days of release from jail will be obtained from patient self-report from the Methadone Treatment Exposure form.

Enrollment in Treatment: will also be obtained from self-report on the Methadone Treatment Exposure form.

Addiction Severity Index (ASI): assesses patient functioning through a 30-45 minute interview covering 7 key domains over the past 30 days including drug and alcohol use, legal, medical, psychiatric and employment status, family functioning and social relations.¹⁰⁶ Composite scores and items from each domain will be investigated (with particular emphasis on drug use and legal scores and items).

Urine Drug Testing: Urine samples will be collected by project staff at 1, 3, 6, and 12 months post-baseline and tested by an approved rapid drug test cup for opiates, methadone, buprenorphine, cocaine, and benzodiazepines. Results will be used for research purposes only and will not be shared with clinic staff.

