However, the PN literature shows that women respond well to this intervention.^{116,117} Therefore, although we anticipate that women will have poorer outcomes than men in the IM alone and detoxification conditions, we hypothesize that women will respond better than men to IM+PN.

Analyses for Aims 1 and 2.

Intent-to-Treat Approach. All analyses will be conducted on available study-related data from all participants (based on their random assignment to treatment condition), regardless of whether or when they drop out of treatment.

Guiding Principle. Although the description of the statistical approach that follows is more in line with the language associated with a ‘traditional’ superiority trial, we endorse the “sensible formulation of the significance test” proposed by Jones and Tukey.¹¹⁸ They outline an approach to significance testing that focuses not on the rejection of a null hypothesis, but on determining whether the data favor a determination of superiority or inferiority. As part of their approach, they suggest reporting not only a test statistic and its associated probability value but also a confidence interval and an effect size related to the determination of any difference. It would be our intention in reporting our results to adhere to Jones and Tukey’s suggestions.

Outcome Variables. Outcome variables will be of three distinct types: 1) dichotomous variables (e.g., entry into treatment, illicit opioid and cocaine urine test results, meeting DSM-5 opioid and cocaine dependence criteria), assumed to follow a binomial distribution; 2) discrete random variables (e.g., number of days of heroin and cocaine use and criminal behavior in the past 30 days), assumed to follow a Poisson distribution; and, 3) continuous random variables (e.g., HIV Risk scale scores), assumed to follow a normal distribution. All distributional assumptions will be evaluated prior to the conduct of all analyses, and if such assumptions are not met, assumptions will be modified and statistical methods chosen accordingly, and/or outcome measures transformed appropriately. For example, it may be necessary to allow for under- or over-dispersion in the logistic and Poisson regression analyses; or a negative binomial model may be more appropriate for the count variables. [In the case of transforming an outcome variable, preference will be given to a transformation that permits clearer clinical interpretation of findings].

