They will be informed that if they are assigned to the interim methadone + patient navigator condition, a study staff member serving as patient navigator will meet with them in the detention center to assess potential barriers to their entry into methadone treatment upon release. They will be told that the navigator will be available to them for three months after release to help them enter and remain in treatment. These services may include help: getting a bus pass, arranging childcare, and referring their significant others to drug abuse treatment. Navigators will also be available to provide advocacy for them with their drug treatment program.

Participants will be informed that they will receive a series of assessments at study entry and at 1, 3, 6, and 12 months post-release. A urine sample will be collected during the assessments in the community. They will be told that all of their urine test data and responses to the assessment questions will be confidential and will not effect their treatment at the detention center or in the community. The limits of confidentiality will be explained including threats of harm to self or others, child or elder abuse, or certain communicable diseases (e.g., tuberculosis). They will be informed that their study involvement requires their consent for the research staff to obtain their methadone treatment data from his/her detention center methadone program record, treatment information from the methadone program in the community that they attend as well as admission, discharge dates from any other public drug treatment programs attended during the course of the study, and their arrest and incarceration records from the criminal justice system.

In addition, participants who provide a signed informed consent addendum will be interviewed at 24-months after enrollment using the same interview and urine collection approach as for the 12-month interview.

Potential risks

Risks of substance abuse. Risks of opioid and/or other substance abuse include: overdose death, infections including but not limited to endocarditis, soft tissue infection, hepatitis, kidney infection, HIV infection, seizure, stroke, and trauma from motor vehicle, machinery, or violence.

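### Treatment entry rests on a single self-reported 1-month interview analysed on available data, with no rule for participants not interviewed, so Contrast 1B on entry is open to bias whose direction the documents do not fix

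*Combined protocol and SAP*

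**What the plan says.** Figure 1 (section 7, Research Interviews) lists "Treatment Entry (self-report from Methadone Treatment Exposure form" with 1 month as its only time point. Measures for Aim 1 and 2 adds that entry "within the first 30 days of release from jail will be obtained from patient self-report from the Methadone Treatment Exposure form".

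Under Analyses for Aims 1 and 2, the Intent-to-Treat paragraph says that "All analyses will be conducted on available study-related data from all participants", by assigned condition and whether or not they leave treatment. That last clause deals with dropping out of treatment, not with a missed interview. The Statistical Method paragraph names a generalized linear mixed model for everything, and entry is listed among the binomial outcomes. I found no missing-outcome rule, imputation or sensitivity analysis.

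On loss to follow-up, the Follow-up and Attrition paragraph says "we expect to obtain follow-up rates of about 90" per cent, not split by arm. Section 6.c says of the navigated arm only: "PNers will seek out participants if they cannot be reached by phone (much the same way that our research staff now does for follow-up interviews".

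Two further sources exist but are not assigned to this outcome. Figure 1 schedules the "Methadone Treatment Exposure Questionnaire" again at 3, 6 and 12 months. Consent (Human Subjects, Participant Recruitment) covers information from the community methadone program attended and "admission, discharge dates from any other public drug treatment programs attended during the course of the study". The Project Timeline plans to obtain participants' treatment records in the closing months.

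**The concern.** Hypotheses 1A and 1B concern entry among participants as randomised. An available-data analysis of a single interview answers a narrower question: entry among those who were found at 1 month. Being found may well depend on the outcome, since someone attending a clinic is likely to be easier to locate. It may also depend on arm, because navigators add a second layer of tracing in IM+PN alone.

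For outcomes measured repeatedly, a mixed model can draw on a participant's other visits. Entry has one record per person, so that protection is absent and the analysis is complete-case. Navigation is aimed directly at entry, so Contrast 1B on entry is where an unhandled denominator problem matters most.

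**Working it through.** **The plan's own figure.** 300 × 0.90 = 270, the N that the Power paragraph uses after attrition. It reproduces. It gives total loss only, with nothing by arm or by entry status.

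**Inputs**
- From the documents: about 10% loss overall; Contrast 1B compares IM+PN with IM alone; entry among inmates started on methadone in jail has ranged from 14% to 50% (rationale for Hypothesis 1B).
- Also from the documents: the parent study's follow-up was "97.9%, 89.4%, and 96.3% at 4 months" for interim, standard and restored methadone (Progress Report, 1.c). Loss was therefore 2.1%, 10.6% and 3.7%.
- Assumed: true entry of 50% in IM alone (top of the cited range) and 65% in IM+PN (the plan states no rate). The allocation of loss to arms is also assumed. The parent figures serve only as plausible magnitudes.

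**Formula.** Let p be the true entry rate, L the share lost and q the entry rate among the lost. The observed rate is (p − Lq)/(1 − L).

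**All lost are non-entrants (q = 0).** The true difference is 15 points and the true odds ratio is (0.65/0.35)/(0.50/0.50) = 1.86.

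| Loss, IM+PN v. IM alone | Observed rates | Difference | Odds ratio |
|---|---|---|---|
| 2.1% v. 10.6% | 0.65/0.979 = 66.4%; 0.50/0.894 = 55.9% | 10.5 points | 1.56 |
| 10% v. 10% | 0.65/0.90 = 72.2%; 0.50/0.90 = 55.6% | 16.7 points | 2.08 |
| 10.6% v. 2.1% | 0.65/0.894 = 72.7%; 0.50/0.979 = 51.1% | 21.6 points | 2.55 |

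**Lost participants enter at half their arm's rate (q = p/2).** In the same order:
- (0.65 − 0.021 × 0.325)/0.979 − (0.50 − 0.106 × 0.25)/0.894 = 0.657 − 0.530 = 12.7 points
- (0.65 − 0.10 × 0.325)/0.90 − (0.50 − 0.10 × 0.25)/0.90 = 0.686 − 0.528 = 15.8 points
- (0.65 − 0.106 × 0.325)/0.894 − (0.50 − 0.021 × 0.25)/0.979 = 0.689 − 0.505 = 18.3 points

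**What drives the bias on the logistic scale.** With q = 0, observed OR = true OR × (1 − r₁)/(1 − r₂). Here r is the share of non-entrants who are missed, in IM alone (1) and IM+PN (2).
- First row of the table: r₁ = 0.106/0.50 = 0.212 and r₂ = 0.021/0.35 = 0.06, so 1.857 × 0.788/0.94 = 1.56.
- If 20% of non-entrants are missed in each arm, loss is 0.20 × 0.35 = 7% v. 0.20 × 0.50 = 10%. The odds ratio stays at 1.86, although fewer are lost in IM+PN. The difference in rates moves only slightly, to 0.65/0.93 − 0.50/0.90 = 14.3 points.

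Unequal loss alone is therefore not enough. The odds ratio is biased when non-entrants are missed at different rates by arm.

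**The case against.** Much in the plan limits the loss. Research assistants trace participants in every arm, and section 6.c describes the navigators' outreach as resembling what research staff already do. Participants who are re-incarcerated are still interviewed and paid, which recovers some likely non-entrants. The model includes arm, gender, age, prior methadone treatment and baseline cocaine use, so loss that depends only on these does no harm. All of this stands. It makes the problem smaller but supplies no rule for those who remain missing.

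A reader might infer more: that those lost will mostly be non-entrants, fewer of them in the navigated arm, so that the navigation effect is understated. The documents do not support that. They say nothing about who will be missed. In the parent study, the arm with 97.9% follow-up was interim methadone (a mean of 0.7 counseling sessions) and the arm with 89.4% was standard methadone (8.3 sessions). Neither had a navigator, and these are 4-month rates, not 1-month rates. Giving the lower loss to IM+PN is a choice. If IM alone keeps interim methadone's 2.1% and IM+PN takes restored methadone's 3.7%, the difference is 0.65/0.963 − 0.50/0.979 = 16.4 points, on the other side of 15.

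Nor can Contrast 1A on entry be sized. The 14% and 50% figures both come from inmates started on methadone, and no entry rate is given for detoxification.

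A fair criticism of any remedy is that scoring everyone missing as not entered brings its own error. Take true entry of 70% v. 50%, 5% v. 15% missing, and 20% of the missing having in fact entered. The scored rates are 0.70 − 0.01 = 69% and 0.50 − 0.03 = 47%, a difference of 22 points against a true 20. That rule therefore belongs last.

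**Conclusion.** The gap is real. One self-reported observation, analysed on available data with no missing-outcome rule, leaves Contrast 1B on entry open to bias if non-entrants are missed at different rates by arm. Navigator tracing in one arm makes that plausible, but the documents do not establish it. Under the assumed 65% v. 50%, a true 15-point difference could appear as anything from 10.5 to 21.6 points across the loss patterns tried when all lost are non-entrants, and 12.7 to 18.3 when the lost enter at half their arm's rate. These figures show how far the result could move. They do not predict a direction, and neither a positive nor a null result on entry should be discounted in advance on their strength. This is worth correcting as a cheap improvement, because a source that does not depend on the interview is already consented to and planned.

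**What to change.** Determine entry within 30 days of release for every randomised participant who is released, in this order:
1. The 1-month self-report, where completed.
2. Otherwise, the community program information and admission dates already covered by consent and due to be obtained.
3. A later Methadone Treatment Exposure form, only where it establishes entry within 30 days. The questionnaire is described as covering treatment status, expected stay and reasons for leaving, so an entry date may not be recoverable.
4. Not entered, for anyone still unresolved.

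Report the number never released by arm, since limiting the denominator to those released is itself a restriction after randomisation. Give the available-data analysis and a tipping-point analysis as sensitivity analyses, with interview follow-up and record-capture rates by arm.

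The cost is a few sentences in the analysis plan and a little data linkage. The main downside is that people who enter programs outside the records are misclassified. This may be more common in the detoxification arm: section 1 (Study Design Issues) expects these participants to face many kinds of program, whereas the IM arms are referred to a few participating clinics. Reporting record capture by arm would help show whether this matters.

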Explanatory Variables. The predictor variables in all statistical models can be categorized as either Treatment Variables, Moderator Variables, or Control Variables.

Treatment Variables: There will be a single treatment variable with three conditions: Intervention Condition [IM+PN v. IM Alone v. Methadone Detoxification (ETAU)].

Moderator Variables: There will be a single moderator variable: Participant Gender.

Control Variables: Three additional predictor variables – participant age, prior methadone maintenance treatment (yes v. no), and self-reported cocaine use at baseline – will be included as “main effects” in all analyses in order to examine for potential differences in treatment outcome as a function of these three variables. (In the parent study: 56% had never previously been in MM treatment; and, self-reported cocaine use at baseline predicted lower treatment retention at 6 months).

Time: Finally, the “repeated factor” in the statistical analysis of all outcome variables measured repeatedly will be assessment Time point, which will allow for the evaluation of both *differential course and impact* of the interventions as a function of the “between-subjects” Treatment Condition factor. (For information regarding which outcome variables are measured at what assessment time points, see **Figure 1. Outcomes and Measures by Aim and Measures**, above).

Planned Contrasts: It is possible to construct two orthogonal, single-degree-of-freedom, planned contrasts that directly test **Hypothesis 1A** and **1B**, respectively. Contrast 1A will compare the two IM treatment conditions (IM+PN and IM Alone, pooled) to the Methadone Detoxification condition. Thus, this comparison directly addresses the question of the differential effectiveness of some form of IM treatment in comparison to a ‘minimally sufficient’ treatment-as-usual (methadone detoxification). Contrast 1B will compare the IM+PN condition to the IM alone condition. Hence, this comparison directly addresses the question of the relative

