effectiveness of the adding PN to IM treatment. Similarly, it is possible to construct two orthogonal, single-degree-of-freedom, planned contrasts that directly test **Hypothesis 2A** and **2B**, respectively. Contrast 2A will compare males and females in the IM+PN condition. Hence, this comparison directly addresses the question of the differential effectiveness of IM+PN treatment for males and females. Contrast 2B will compare males and females in the IM Alone and Methadone Detoxification conditions, pooled. Thus, this comparison directly addresses the question of the differential effectiveness of non-PN treatments for males and females. Given that both the course and impact of treatment are important to evaluate, planned contrasts can be examined both as each interacts with the “repeated factor” of Time (when there is a repeated factor), and as a “simple effect” at a given time point, in the event either Contrast X Time interaction effect proves to be significant.

AIM 3: To conduct a focused cost-effectiveness and cost-benefit study of the three treatment conditions

HYPOTHESIS 3a (Cost Hypothesis). IM alone will have greater treatment costs per person than detoxification. Furthermore, IM+PN will have greater treatment costs per person than IM alone.

HYPOTHESIS 3b (Cost-Effectiveness Hypothesis). IM+PN will yield better outcomes relative to the IM alone which in turn will yield better outcomes than detoxification in terms of higher rates of treatment entry and longer retention in treatment, and greater reductions in illicit opioid and cocaine use, decreased likelihood of meeting DSM-5 criteria for opioid and cocaine use disorders, decreased HIV risk behavior, and decreased criminal behavior, arrest, and incarceration. The better outcomes for IM+PN justify the greater costs of IM+PN compared to IM alone, making IM+PN cost effective compared to IM alone.

HYPOTHESIS 3c (Cost-Benefit Hypothesis). IM alone will yield greater economic benefit in terms of criminal activity, health care utilization, and employment in the 12-month post-release period relative to its costs relative to the detoxification condition. Furthermore, IM+PN will yield greater economic benefits than IM alone.

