Assuming $\alpha=.01$ and $N=300$, the resulting SAS GLIMMIX power estimates ($1 - \beta$) for the four planned contrasts X Time (see *Planned Contrasts*, above; for retained in treatment and arrest and incarceration, the effect of interest was necessarily the four planned contrasts themselves, as there was no Time effect for this outcome) associated with **Hypothesis 1A, 1B, 2A, and 2B** exceeded .81 in all cases, assuming “small” differences associated with each such effect, and even assuming an unstructured covariance matrix. For the set correlation approach, and in this case assuming $N=270$ due to attrition (see *Follow-up and Attrition*, above) in order to remain conservative, an effect size in the population associated with a Planned Contrast X Time for **Hypothesis 1A, 1B, 2A, and 2B** of $f^2=.048$ (.094 for retained in treatment and arrest and incarceration) would yield a power of .9 for that effect. [All 4 Planned Contrasts X Time for **Hypothesis 1A, 1B, 2A, and 2B** have the same degrees of freedom, so yield a common effect size.] The effect size involving the Time effect falls in the “small” range, while the effect size that does not include a Time effect falls in the “small-to-medium” range, with $f^2=.02$ considered a “small” effect and $f^2 = .15$ a “medium” effect.¹²¹

9. Process Evaluation.

9.a. Need for Process Data: Due to the key role of PN in this study for overcoming barriers associated with community re-entry (**Aim 1**), particularly for women (**Aim 2**), we will conduct a qualitative process evaluation that will examine PN experiences in detail.

9.b. Qualitative Sample Selection: Using purposive sampling, a subset of 32 participants (16 IM+PN and 16 IM alone) will be selected to complete semi-structured qualitative interviews. Participant selection will emphasize heterogeneity in order to examine the views and experiences from as diverse a sub-sample as possible and will include an equal number of men and women from each condition. The proposed sample size will ensure that saturation is likely to be achieved (i.e., bringing new participants into the study until the data set is complete, as indicated by data replication or redundancy) and should allow for the extraction of thick, rich data

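### Where a varying baseline is collected, the plan neither adjusts for it nor equates it across arms, and it does not say whether baseline is a level of Time

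*Combined protocol and SAP*

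**What the plan says.** Under Analyses for Aims 1 and 2, Explanatory Variables, the predictors are condition, gender and three control variables: age, prior methadone maintenance (yes or no) and self-reported cocaine use at baseline. The control variables enter all analyses as main effects. The repeated factor "in the statistical analysis of all outcome variables measured repeatedly will be assessment Time point", with a pointer to Figure 1 for which outcome is measured when.

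Under Planned Contrasts, "planned contrasts can be examined both as each interacts with the" repeated factor, and as a simple effect at a given visit if such an interaction is significant. Statistical Method adds only that a generalized linear mixed model is used throughout.

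Figure 1 has separate Baseline and Follow-up columns. It marks baseline for the row "Illicit Opioid and Cocaine Use (ASI and urine drug testing"), and for DSM-5 criteria, criminal behavior, RAB and WHOQOL-BREF. ASI drug use, ASI criminal behavior and WHOQOL have four follow-ups, DSM-5 criteria three, and RAB two (6 and 12 months).

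No section says whether baseline is a level of Time, makes the outcome's own baseline a covariate (cocaine use apart), or sets the arms' baseline means equal.

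**The concern.** Randomization makes the arms' baseline means equal in expectation. A model that ignores this estimates a quantity already known, and the noise in that estimate passes into the treatment effect.

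If baseline is a Time level with a free mean in each arm, Contrast X Time is a difference in change from baseline and carries the full baseline noise. If Time means follow-up visits only, the baseline is not used at all (cocaine use apart). Contrast X Time then asks only whether the arm difference varies between follow-up visits. On either reading the visit-level simple effect is not adjusted for that outcome's baseline, and the plan reaches it only through a significant interaction.

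The control variables do little to help. They are constant over time and enter as main effects, so in a linear model they largely cancel out of the interaction.

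At stake is the precision of contrasts 1A and 1B for heroin-use days, crime days and HIV risk, using data the trial already collects.

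**Working it through.** **Inputs.** From Power: alpha .01; N = 300, or 270 after attrition (about 90 per arm); simulated power that "exceeded .81 in all cases"; and a set-correlation effect size f² = .048 (.094 without a Time effect) that "would yield a power of .9 for that effect". Assumed: two-sided testing, normal outcomes, equal variances, compound symmetry, and a baseline-to-follow-up correlation r from .2 to .7. The documents give no r, SD or event rate.

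**1. The plan's own figure.** Noncentral F with λ = f²(u+v+1), alpha .01, N = 270:
- One-df contrast: f² = .048 gives power .84; power .90 needs .056.
- One contrast by 4 Time df: f² = .048 gives .63; power .90 needs .079.
- Two treatment df by 4 Time df (u = 8, v = 528): f² = .048 gives .90.

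The last match fits five Time levels including baseline, but the plan does not state it. One-sided alpha .01 with 1 df also gives about .048. The value .094 fits only u of about 7. The simulated power cannot be rebuilt without SDs, rates or correlations. So the stated figures do not settle whether baseline is a Time level.

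**2. Variance of an arm difference at one visit** (units of 2σ²/n):
- visit only: 1
- change from baseline: 2(1-r)
- baseline-adjusted: 1-r²

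Adjusted over change is (1-r²)/[2(1-r)] = (1+r)/2. Adjusted over visit-only is 1-r². Power below is for contrast 1B, 90 v 90, with an illustrative true difference of 0.5 SD.

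| r | adjusted/change | adjusted/visit-only | power: visit-only / change / adjusted |
|---|---|---|---|
| .2 | .60 | .96 | .78 / .53 / .80 |
| .3 | .65 | .91 | .78 / .60 / .83 |
| .5 | .75 | .75 | .78 / .78 / .90 |
| .7 | .85 | .51 | .78 / .96 / .98 |

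Below r = .5, change from baseline is less precise than ignoring baseline altogether.

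Taking the plan's floor of .81 for a 1-df change test, λ = (2.576 + .878)² = 11.93. Dividing by (1+r)/2 gives power .96, .92 and .88 at r = .3, .5 and .7.

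**3. Joint Contrast X Time test, if baseline is a Time level.** With k follow-ups and a constant effect, information is k/[(1-r)(1+k)] with free baseline means and k/[(1-r)(1+kr)] with adjustment. The ratio is (1+k)/(1+kr).
- k = 4 (ASI, WHOQOL): 5/2.2, 5/3, 5/3.8 = 2.27, 1.67, 1.32 at r = .3, .5, .7. From power .81 on 4 df this gives .998, .98, .93.
- k = 4, effect fading as 1, 1, .5, .25: ratios 1.60, 1.32, 1.15; power .97, .93, .88.
- k = 2 (RAB), constant effect: 3/1.6, 3/2, 3/2.4 = 1.88, 1.50, 1.25.

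**4. If Time excludes baseline.** A constant effect adds nothing to the interaction, so its power equals alpha, 1%. For 0.5 SD at the first two visits and half that at the last two (90 v 90, 3 df), power is .14, .17, .26 and .50 at r = .2, .3, .5 and .7.

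**The case against.** A reader might infer that baseline is a free Time level for every repeated outcome and never a covariate. The documents do not support that:
- Baseline cocaine use is in every model, so simple effects on cocaine use are adjusted. Only the interaction test gains little from it.
- Treatment enrollment and overdose have no baseline mark. The Urine Drug Testing text lists follow-up samples only; the baseline mark sits on a combined ASI/urine row. Opioid use disorder is an inclusion criterion, so its baseline is constant. Treatment entry, which together with retention leads hypotheses 1A and 1B, is measured once.
- That baseline is a Time level is an inference from the text plus Figure 1. Power says arrest and incarceration have no Time effect, although Figure 1 gives them baseline and 12-month values. That points to Time meaning follow-up visits only, in which case steps 2 and 3 on change from baseline do not apply.

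The size is also open to challenge. Days of use and crime are to be modelled as counts and DSM-5 criteria as binary, so normal-theory variances are approximate. The power run assumed an unstructured covariance, not compound symmetry. Under Hypothesis 1B the plan itself anticipates attenuation at 6 and 12 months, so the constant-effect figures are optimistic. If r is low, adjustment gains little over a plain visit comparison: 4% of variance at r = .2 and 9% at r = .3.

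All of this stands and limits the scope and size. It does not remove the gap: for outcomes with a varying baseline, neither reading of Time uses that baseline efficiently.

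**Conclusion.** The point holds for ASI heroin-use days and criminal behavior, RAB, WHOQOL and DSM-5 cocaine criteria, and for cocaine use in the interaction test only.

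If baseline is a Time level, adjustment lowers the per-visit variance of the tested effect by 35%, 25% or 15% at r = .3, .5 or .7. If it is not, Contrast X Time has no power against an effect constant across visits beyond its 1% alpha. On either reading the simple effect gives up r² of its variance (9%, 25%, 49%), cocaine use excepted.

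These sizes rest on an r that the documents do not give, are exact only for normal outcomes, and for the joint test shrink with fewer visits. A reader might go further and infer that the contrasts are biased or that the stated power is wrong. Neither follows: randomization keeps the unadjusted contrasts 1A and 1B valid, and the plan's simulation inputs are not given. This is an avoidable loss of efficiency and an unstated model choice that should be settled before analysis.

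**What to change.** State for each repeated outcome whether baseline is a level of Time. Then, for contrasts 1A and 1B, where baseline is collected and varies, do one of two things:

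1. Use follow-up visits only as responses, with the outcome's baseline and baseline x Time as covariates. Test the contrast averaged or jointly over follow-up visits as well as Contrast X Time, because the interaction alone misses a constant effect.
2. Keep baseline in the response and constrain the three conditions to a common baseline mean within gender. Add control variable x Time terms. When cocaine use is the response, drop baseline cocaine use as a covariate so that it is not on both sides.

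Omit this for treatment enrollment, overdose, urine results if collected only at follow-up, and opioid use disorder. With a constant baseline, the covariate is collinear with the intercept and a logistic baseline mean cannot be estimated. Do not constrain baseline across men and women for contrasts 2A and 2B, since gender is not randomized. In logistic models, label the adjusted effect as conditional on baseline.

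The cost is model wording only, with no new data. Under either option, arm differences at baseline are shown in the baseline table instead of the model.
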